Arm B – **Daily oral TDF/FTC** and IM placebo (matching vehicle, identical volume as active injectable product in Arm A) at two time-points four weeks apart and every eight weeks thereafter plus an HIV prevention package including behavioral risk reduction and adherence counseling, provision of condoms.

Step 2 will continue until the required number of endpoints (114) is reached, estimated to be 81 weeks after enrolling the last participant.

Participants who prematurely discontinue blinded study products during Step 2 (having received at least one injection) for any reason other than HIV infection will be offered to transition to 48 weeks of open-label TDF/FTC followed by annual testing through the duration of step 3.

A participant who becomes HIV-infected during Step 2 of the study will permanently discontinue study product, be placed on immediate suppressive ART, and will be facilitated into locally provided ART, and followed at quarterly intervals for 48 weeks after

their last injection prior to diagnosis of HIV in order to test for safety parameters, as well as CD4 cell count and HIV viral load. After 52 weeks, they will be terminated from the study and transitioned to continued HIV-related care.

2.7.3 Step 3, Follow-up Phase:

Arms A and B – Open-label daily TDF/FTC (in order to cover the pharmacokinetic [PK] tail for Arm A participants) will be provided no later than eight weeks after the last injection visit, for up to 48 weeks plus an HIV prevention package including behavioral risk reduction and adherence counseling, and provision of condoms. Participants will then transition to locally available HIV prevention services, including services for PrEP, if available.

Participants with confirmed HIV infection during Step 3 will have their TDF/FTC stopped and be followed quarterly at least for the duration of Step 3, with possible additional assessments and follow-up to be determined by guidance from members of the HIV alias. Study product will be discontinued and participants will be referred for care.

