4. STATISTICAL CONSIDERATIONS

4.1 Sample Size and Power

The primary analysis will be based on HIV incidence during Steps 1 and 2. As described previously, we assume that participants will be followed between 81 (latest enrollees) and 185 (earliest enrollees) weeks in Steps 1 and 2 (1.6 – 3.6 years), with a uniform distribution of enrollments over a two-year period. Thus, average time in Steps 1 and 2 will be 133 weeks (2.6 years). Sample size calculations are based on the following assumptions:

- Background HIV incidence, in the absence of any PrEP, is 3.5% per year
- Both CAB LA and TDF/FTC are 85% effective when used with 100% adherence
- 2.5% one-sided type I error rate and 90% power at the indicated alternative
- Average follow-up duration of 2.6 years (range: 1.6 – 3.6 years)
- Maximum 5% lost-to-follow-up per year

Table 4.1 presents five scenarios and associated total sample sizes. All are superiority designs. The first scenario assumes that adherence to TDF/FTC and CAB/CAB LA will be 50% and 85%, respectively, averaged over the entire Step 1 and 2 follow-up period. The second and third scenarios assume a higher adherence to TDF/FTC (second line) and lower adherence to CAB LA (80%) (third line) (these scenarios are considered unlikely). The last two scenarios retain the conservative assumption of 80% adherence to CAB LA and assume lower adherence to TDF/FTC of 45% and 48%. The largest blinded trials of TDF/FTC among women in a similar setting have shown even lower adherence than assumed in Table 4.1.

Given this history we believe that a sample size of at least 3,128 (111 events for a fixed sample size trial; we will target 114 events to allow for interim monitoring) provides an adequate degree of robustness against uncertainties in adherence rates to the two drug regimens. The trial will continue until we reach 114 events, or a stopping boundary is crossed (see below).

Table 4.1. Five Case Scenarios

Adherence		HIV Incidence (%/year) ¹				
TDF/FTC	CAB LA	TDF/FTC	CAB LA	RR	Number Events	Sample Size
.50	.85	2.01	0.97	.48	78	2352
.55	.85	1.86	0.97	.52	98	3112
.50	.80	2.01	1.12	.56	125	3590
.48	.80	2.07	1.12	.54	111	3128
.45	.80	2.16	1.12	.52	98	2686

¹Background incidence is reduced by a weighted average of fully adherent and non-adherent individuals e.g. 2.01 = $3.5 * ((1 - .85) * .5 + 1 * (1 - .5))$

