4.2 Randomization

Participants will be randomized to one of two study arms in a 1:1 ratio. Randomization will be stratified by study site, and a permuted blocks design will be used to ensure balanced treatment assignments within study site. The randomization scheme will be generated, operationalized and maintained by the HPTN Statistics and Data Management Center.

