7.3. Endpoint Analyses

7.3.1. Primary Efficacy Analysis

Objective: To evaluate the relative efficacy of oral CAB/CAB LA (oral run-in and injections, Steps 1 and 2) vs. daily oral TDF/FTC for HIV prevention

Population: mITT population

Outcome: Time of HIV-1 Infection (censored at end of step 2)

Time from randomization to HIV-1 infection (see definition in appendix B) will be the primary endpoint for this analysis. HIV-1 status will be assumed to be negative for any missing visits prior to the first positive HIV-1 test (unless defined differently by the endpoints committee prior to analysis). Person-time and HIV events will be included in this analysis based on each individual's scheduled participation in steps 1 and 2, as determined at randomization. Specifically, individuals who refuse/discontinue injections, pills or both, or who receive open-label study product (e.g. due to pregnancy) will be included in this analysis in their original randomization arm for the duration of their originally scheduled participation in Steps 1 and 2. Individuals who drop out of the study and refuse further testing prior to completion of follow-up and individuals who die prior to completion of follow-up will be treated as uninformatively censored as of their last valid HIV test.

Descriptive analysis: The number of participants, number of infections and cumulative person-years will be presented by arm and overall. The HIV incidence rate will be calculated as the total number of participants with confirmed incident HIV infection during steps 1 and 2 of study follow-up, divided by the person-years accumulated in each arm. Corresponding 95% CIs will be calculated based on Poisson assumptions. Cumulative incidence over follow-up for each arm will be computed using product limit estimates and plotted with 95% CIs.

Statistical Analysis: The primary “intent-to-treat” analysis will be based on a Cox model using time to HIV detection (as defined above) as the outcome. The model will include an indicator for intervention arm (TDF/FTC = 0; CAB LA = 1) and be stratified by site. Consistent with an intent-to-treat analysis, women will be included in the analysis in their original randomization group whenever endpoint information is available within the prespecified timeframe of follow-up. Participants who remain HIV-1 uninfected will be censored at their last negative HIV test. A formal statistical comparison between study arms will be performed using a Wald test of the hypothesis

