
Ho: HR = 1

Ha: HR < 1

A two-sided test with $\alpha = .05$ will be used. The estimated hazard ratio (HR), a 95% confidence interval, and a p-value for the hypothesis shown above will be given. If the number of events is small (<40) then the p-value will be confirmed using a permutation test based on 100,000 random permutations of the treatment assignments; if there is a meaningful difference between the permutation and asymptotic procedures, the permutation p-value will be used. Treatment efficacy will be estimated as $TE = 1 - HR$.

If the trial is stopped early (prior to the final analysis), then the primary results will be reported as a bias-adjusted mean HR and design-adjusted 95% CI (Emerson S and Fleming TR. Symmetric Group Sequential Test Designs. *Biometrics* 45:904-923, 1989).

7.3.1.1. Sensitivity of the Primary mITT results:

The following sensitivity analyses are proposed to aid in interpretation of the primary ITT results :

- A per-protocol analysis, excluding participants with exclusionary protocol violations, will be conducted if the number of participants affected exceeds 2% of the enrolled population.
Population: Per Protocol
This analysis will be identical to the mITT analysis, except that for partial exclusions, the follow-up will be censored on the last non-missing HIV test result date on or prior to the date of the deviation that resulted in exclusion from the per-protocol population.
- A supportive analysis will be presented using the OBSP censoring in the Injection (Step 2) Efficacy population (see OBSP censoring definitions in appendix B), where study follow-up is censored when a participant does not receive blinded injection study product on time.
- In this active control trial, the superiority of CAB LA is predicated in part on incomplete adherence to daily oral TDF/FTC. Specifically, we assume that overall adherence to TDF/FTC will be less than 50%. If adherence to TDF/FTC is high (greater than 50%) then, as described in section 7.8.4 of the protocol, a supportive non-inferiority (NI) analysis of CAB LA versus TDF/FTC may provide valuable information for interpreting the trial results.

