Adherence in the TDF/FTC arm will be measured during the trial in an adherence assessment cohort (see below). If adherence in the TDF/FTC arm is greater than 50% then an NI margin will be computed as described in section 7.8.4.3 of the protocol. The primary analysis described above will then be repeated using the recomputed NI margin instead of 1.0 in the null hypothesis. This supportive NI analysis will not replace the pre-specified primary analysis or change the conclusion of the primary analysis but may provide valuable insight with respect to determining the prevention effectiveness of CAB LA in women.

7.3.1.2. Adherence Assessment Cohort:

A sample of 400 participants in the active TDF/FTC arm will be selected at random during the enrollment period and available plasma samples from selected visits (Step 1: week 4; Step 2: weeks 9, 17, 33, 57, 81, 105, 129, 153, 177) will be assessed for the presence of TDF/FTC and associated metabolites. The TDF/FTC adherence-assessment cohort will be stratified by site or

region and will be selected to ensure uniform representation over the course of the enrollment period. Average, study-wide adherence will be computed as the overall proportion of all tested samples where study drug (TDF/FTC) is detected (i.e. concentrations greater than approximately 0.31 ng/ml).

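### As written in the SAP, the supportive non-inferiority test uses only the mITT analysis, which counts CAB-arm time on open-label TDF/FTC as CAB time; the planned OBSP hazard ratio should be read against the same margin.

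*SAP*

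**What the plan says.** SAP section 7.3.1.1 makes the NI analysis conditional on measured TDF/FTC adherence above 50%. The margin is to be computed as set out in protocol section 7.8.4.3, and then "The primary analysis described above will then be repeated using the recomputed NI margin instead of 1.0 in the null hypothesis". The SAP calls the analysis supportive and says that it cannot replace or change the primary conclusion.

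The analysis being repeated is that of section 7.3.1, on the mITT population. There, women who stop injections or pills, "or who receive open-label study product (e.g. due to pregnancy) will be included in this analysis in their original randomization arm", for as long as they were originally scheduled to be in Steps 1 and 2.

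Sections 2.7.2 and 2.7.4 say what that open-label product is:
- Women who stop blinded product early in Step 2 after at least one injection, for reasons other than HIV infection, "will be offered to transition to 48 weeks of open-label TDF/FTC".
- Women with a confirmed pregnancy go onto open-label TDF/FTC, whichever arm they were assigned to.
- Women who decline contraception receive open-label TDF/FTC for 48 weeks.

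Section 7.3.1.1 lists an on-product analysis separately: "A supportive analysis will be presented using the OBSP censoring in the Injection (Step 2) Efficacy population". The SAP does not say that this result is compared with the NI margin.

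**The concern.** For a CAB-arm woman who leaves injections, the replacement drug is usually the comparator. While she takes it, her person-time and any infection still count as CAB LA. In a superiority test this dilution is conservative. In an NI test it is not conservative when CAB LA is truly worse: the two arms look more alike because part of the CAB arm is taking TDF/FTC.

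The SAP wants this analysis to inform the prevention effectiveness of CAB LA when TDF/FTC adherence is high. An NI statement resting on mITT alone could then owe something to comparator use in the CAB arm, and a reader could not see how much.

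The per-protocol analysis does not fill the gap. It is built on adjudicated deviations and run only if more than 2% of enrolled participants are affected. Moving to open-label TDF/FTC is planned management, so that set does not by itself remove crossover time. OBSP censoring largely does.

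**Working it through.** **1. The plan's own figure.** The SAP states no event number for the NI test, so the superiority figure is checked to confirm the scale. Inputs: HR 0.54 (section 4.1.1), "2.5% one-sided type I error rate and 90% power at the indicated alternative" (section 4.1), and 1:1 allocation (section 4.2).

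Events = 4 × (1.960 + 1.282)² / (ln 0.54)² = 4 × 10.51 / 0.3797 ≈ 111.

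This matches the SAP: "111 events for a fixed sample size trial; we will target 114 events to allow for interim monitoring". The approximation SE(ln HR) = 2/√events is therefore the plan's own scale.

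**2. Effect of crossover.** Let M be the NI margin and c the share of CAB-arm person-time on open-label TDF/FTC. Both are assumptions. If that time carries the TDF/FTC-arm hazard:

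- HR in mITT = (1 − c) × true HR + c
- Probability of an NI finding = Φ[ (ln M − ln HR in mITT) × √D / 2 − 1.96 ], with D events

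The value 1.96 follows from the primary test: "A two-sided test with $\alpha = .05$ will be used".

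**3. False-NI rate when the true HR equals the margin (nominal 2.5%).** Worked case with M = 1.3, c = 20%, D = 114: HR = 0.8 × 1.3 + 0.2 = 1.24; ln(1.3/1.24) = 0.0473; × √114/2 (5.339) = 0.252; Φ(−1.708) = 4.4%.

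| Margin (assumed) | Events | c = 10% | c = 20% |
|---|---|---|---|
| 1.1 | 114 | 2.8% | 3.1% |
| 1.23 | 114 | 3.2% | 4.0% |
| 1.3 | 114 | 3.3% | 4.4% |
| 1.5 | 114 | 3.8% | 5.6% |
| 1.23 | 60 | 3.0% | 3.5% |
| 1.5 | 60 | 3.4% | 4.5% |

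**4. Chance of an NI finding when CAB LA is as good or better (M = 1.23, D = 114).**

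| True HR | c = 0 | c = 20% |
|---|---|---|
| 0.54 | 0.993 | 0.945 |
| 0.80 | 0.632 | 0.530 |
| 1.00 | 0.196 | 0.196 |

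Below 1, crossover works against NI. At 1 it has no effect.

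**5. When the HR would exceed 1.** The footnote to Table 4.1, with both drugs 85% effective at full adherence, gives HR = (1 − 0.85 × CAB adherence) / (1 − 0.85 × TDF/FTC adherence). With CAB adherence of 80% the numerator is 0.32:

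- TDF/FTC adherence 55%: 0.32/0.5325 = 0.60
- 70%: 0.32/0.405 = 0.79
- 80%: 0.32/0.32 = 1.00
- 90%: 0.32/0.235 = 1.36

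On the plan's own assumptions, the HR passes 1 only when TDF/FTC adherence is higher than CAB adherence. The 50% trigger reaches that region, but it also covers a wide range in which the HR is below 1.

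**The case against.** Several points on the other side have force.

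- **A reader might infer that crossover generally favours an NI finding.** The documents do not support that. It does so only if the true HR is above 1, and steps 4 and 5 show that over much of the range that triggers the analysis the effect runs the other way.
- **A reader might infer that no on-product NI comparison exists anywhere.** The SAP refers to protocol section 7.8.4 for the details of the NI analysis. That section was not at hand and may add one. The point still stands for the SAP, because section 7.3.1.1 itself says which analysis is repeated. If the protocol adds another, the SAP should point to it.
- **The HR during open-label time need not be 1.** Section 2.7.3 gives TDF/FTC to cover the CAB pharmacokinetic tail, so switchers may carry residual CAB. After 48 weeks discontinuers move to annual testing. After pregnancy and breastfeeding, women may resume their assigned product open-label. The mixing formula ignores all of this and is only approximate.
- **OBSP is not a clean remedy.** Appendix B censors on late injections, which are placebo in the TDF/FTC arm. It removes CAB-arm women who are late for active drug but keeps TDF/FTC-arm women who miss pills, an asymmetry that can favour CAB. The population is also selected after randomization. Censoring at crossover restores the 2.5% rate only if it is uninformative.
- **Keeping women in their randomized arm is coherent for effectiveness**, which is the purpose that the SAP states.

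The last two points tell against replacing mITT, or making NI formally depend on success in both sets. They do not tell against showing both results.

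**Conclusion.** The point holds as a modest reporting gap. On the SAP's wording, the NI test is specified for mITT only, CAB-arm time on open-label TDF/FTC counts as CAB, and the one planned analysis that largely removes that time is not tied to the margin.

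If the true on-product HR equals a margin above 1, the one-sided false-NI rate rises from 2.5% to about 2.8 to 5.6% with 114 events. That range rests on assumed margins of 1.1 to 1.5, assumed crossover shares of 10 to 20%, and switchers having the TDF/FTC-arm hazard. Larger values need stronger assumptions: 8.1%, for example, requires a margin of 1.5 and a 30% share. The documents give no margin and no share, so no single figure can be defended.

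Neither the primary superiority analysis nor its conclusion is affected.

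**What to change.** In SAP section 7.3.1.1, add to the NI paragraph:

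1. The OBSP-censored HR in the Injection (Step 2) Efficacy population, with its upper confidence limit, will also be compared with the same NI margin and reported beside the mITT NI result.
2. If the two disagree, the result will be interpreted cautiously, and an NI statement will not rest on mITT alone.
3. The share of mITT person-time on open-label TDF/FTC will be reported by arm, counted separately from open-label CAB LA.

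If protocol section 7.8.4 already provides an on-product NI comparison, a cross-reference would serve for item 1.

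The cost is a few sentences and one extra tabulation, since the OBSP model is already planned. The downside is that the OBSP set will have fewer events and a wider interval, is not fully protected by randomization, and censors on injection timing only. The text should state these limits, so that OBSP is read as a complement to mITT and not as a substitute.

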7.3.2. Primary Safety Analysis

Objective: To evaluate the relative safety of oral CAB/CAB LA (oral run-in and injections, Steps 1 and 2) vs. daily oral TDF/FTC for HIV prevention (Steps 1 and 2).

Population: Safety population

The primary pre-specified safety comparison between arms will be based on all AEs with maximum grade ≥ 2 . In general, formal statistical comparison of individual types of safety events across arms is not planned since interpretation of differences must rely heavily upon clinical judgment. Where formal statistical testing is considered necessary to guide judgement of observed differences for any single event or collection of events, differences in events grade 2 and higher will be assessed. The event rate and 95% robust confidence interval for each treatment arm will be calculated using a log-linear model for counts using log(person-time) as an offset, treatment as a covariate, assuming a Poisson distribution and using a robust variance (i.e. generalized estimating equations). Event rates will be compared between treatment arms using this same model. Event rates will be compared between treatment arms using this same model and a type I error rate of $\alpha=0.05$ is prespecified. Very rare events will be compared using an exact Poisson test. Additional supporting descriptive safety analyses will be presented.

For Safety OBSP analysis, adverse event follow-up will be censored after the last injection before a termination or a permanent product discontinuation regardless of any delays in injections. If termination or a permanent product discontinuation occurs prior to their first injection, the participant's follow-up time will be censored at the termination or permanent product discontinuation date +1. If termination or a permanent product discontinuation occurs after the first injection, the participants follow-up time will be censored up through 6 weeks after the Week 5 injection, if that is the last injection, or 10 weeks after the last injection for subsequent injections.

7.3.3. Adverse events in Step 1

Objective: To compare the safety of oral CAB vs. oral TDF/FTC in Step 1

Population: Primary Safety

Censoring: AEs are censored at 120 days after randomization for participants who never received an injection; at 1 day after the date of termination or investigational product discontinuation; at date of first injection, whichever occurs first. Reported AEs will be excluded if they occur after the censoring time.

Descriptive and Statistical Analysis as above

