7.3.4. Adverse events Step 2 only OBSP

Objective: To compare the safety of CAB LA vs. oral TDF/FTC proximal to blinded study drug administration

Population: Step 2 safety

Censoring: AEs are censored using ON BLINDED STUDY PRODUCT (OBSP) censoring.

Details of the OBSP censoring definitions are given in Appendix B. Reported AEs will be excluded if they occur before the first injection or after the OBSP censoring time.

Descriptive and Statistical Analysis will be performed as above

7.3.5. *Laboratory evaluations*

Population: Primary Safety

Descriptive: Laboratory findings for CBC, chemistries (urea, creatinine, CPK, glucose, calcium, phosphorous, amylase, lipase), liver function (AST, ALT, total bilirubin, alkaline phosphatase) and fasting lipid profile (total cholesterol, triglycerides, HDL, LDL) will be reported by grade, as defined in the “Division of AIDS (DAIDS) Table for Grading the Severity of Adult and Pediatric Adverse Events”. The proportion of laboratory findings qualifying as Grade 2 or above will be presented. Laboratory values will be reported by arm as median, 1st and 3rd quartiles, min and max, and (at follow-up visits) as median, 1st and 3rd quartile change from baseline (see below). Summaries involving values and changes from baseline at scheduled visit time points will consider values from scheduled visits only, and in the case of missing values, results will not be carried forward from interim (unscheduled) visits. For summaries and analyses involving changes in laboratory values over time or maximum change from baseline (e.g. shift tables), values from interim (unscheduled) visits will also be considered.

Formal comparisons of laboratory values will be conducted as follows:

- Absolute values: A mixed-effects model with participant as the random effect and site and arm as fixed effects will be used to assess overall differences in each laboratory outcome by arm. Outcomes with highly skewed distributions will be log-transformed. A continuous time (elapsed study time) term and an interaction of time with study arm will be added to model time trends in laboratory values that may emerge with continuous exposure to study drug. Only post baseline visits will be included.

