- Change from baseline. A fixed effect model with site and arm as covariates will be used to assess overall change from baseline for each laboratory outcome by arm. A continuous time (elapsed study time) term and an interaction of time with study arm will be added to model differences in laboratory values that may emerge with continuous exposure to study drug.

Note: Formal comparisons of laboratory values as described above will not be included in the Clinical Study Report.

7.3.6. *Secondary Analyses*

- a. **Objective:** To compare HIV incidence among participants receiving oral CAB/CAB LA vs. daily oral TDF/FTC (Steps 1, 2 and 3).

Population: mITT population

Outcome: Time of HIV-1 Infection

This analysis will be similar to the primary analysis of HIV incidence but will include the entire follow-up period (steps 1, 2 and 3) for each participant. The analysis will be based on a Cox model using time to HIV detection (as defined in the primary analysis) as the outcome. The model will include an indicator for intervention arm (TDF/FTC = 0; CAB LA = 1) and be stratified by site. Participants who remain HIV-1 uninfected will be censored at their last negative HIV test. A formal statistical comparison between study arms will be performed using a Wald test of the hypothesis

Ho: HR = 1

Ha: HR < 1

A one-sided test with $\alpha = .025$ will be used. The estimated hazard ratio (HR), a 95% confidence interval, and a p-value for the hypothesis shown above will be given.

b. **Objective:** To evaluate relative efficacy of oral CAB/CAB LA vs. oral TDF/FTC in subgroups defined by the baseline factors of age, herpes simplex virus-2 (HSV-2) serostatus, and body mass index (BMI).

Population: mITT population

Outcome: Time of HIV-1 Infection

These analyses will be similar to the primary analysis of HIV incidence and will include data from follow-up steps 1 and 2 for each participant. The number of events, person-years and incidence will be calculated for each arm within each subgroup.

Subgroups will be defined as follows:

Age (<25 vs ≥ 25)

HSV-2(positive or negative)

BMI (<30.0 vs ≥ 30.0)

Contraceptive method during treatment (DMPA, Net_EN, Implants, Other)

Age, HSV-2 and BMI will be based on baseline status while contraception will be treated as a time-varying covariate.

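### The 0.05-level comparison of grade 2 or higher AE rates omits site, the randomization stratum, so its interval is too wide if site AE rates differ

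*SAP*

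**What the plan says.** Section 7.3.2 names the comparison of AEs of maximum grade 2 or higher as the primary prespecified safety comparison. Arm-specific rates and confidence intervals are "calculated using a log-linear model for counts using log(person-time) as an offset, treatment as a covariate, assuming a Poisson distribution", "using a robust variance (i.e. generalized estimating equations"). The comparison sentence appears twice in a row; the second time it reads "Event rates will be compared between treatment arms using this same model and a type I error rate of" 0.05. No other covariate is named. Section 7.3.3 takes the method over ("Descriptive and Statistical Analysis as above"), and section 7.3.4 does so in similar words.

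Section 4.2 says: "Randomization will be stratified by study site, and a permuted blocks design will be used". Other models in the SAP use that stratum:

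- The primary Cox model in 7.3.1 is to "be stratified by site", as are the Steps 1–3 and subgroup Cox models in 7.3.6.
- For absolute laboratory values, 7.3.5 states: "A mixed-effects model with participant as the random effect and site and arm as fixed effects will be used".
- For change from baseline, 7.3.5 states: "A fixed effect model with site and arm as covariates will be used".

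The SAP gives no reason for leaving site out of 7.3.2.

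**The concern.** Permuted blocks within site balance the arms inside each site. Differences in AE rates between sites therefore largely cancel out of the arm contrast, and its true sampling variance is smaller than under simple randomization. A robust variance computed per participant from a model without site does not recognise this. It treats the spread of site rates as participant-level noise and adds it to the standard error.

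At stake is the accuracy of the reported precision, not the validity of the estimate. In a safety comparison a conservative test is not the cautious choice, because it makes a modest AE difference between CAB and TDF/FTC harder to show. The other log-linear rate models in 7.3.7 (STIs, AEs by BMI, pregnancy) also lack a site term, but 7.3.2 is the only one of them for which the SAP sets an alpha for a between-arm test.

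**Working it through.** **Inputs from the SAP.** 3,350 women (4.4); 1:1 allocation and site-stratified permuted blocks (4.2); follow-up of 1.6 to 3.6 years with uniform enrolment (4.1); alpha 0.05 (7.3.2, sidedness not stated, taken as two-sided).

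**Assumed, because the text at hand gives no figure.** 20 sites (Appendix D lists them but is not in the text available for review, so this is not a gap in the SAP); blocks of 6; mean m = 3 events per woman; participant-level overdispersion k = 0.7; between-site coefficient of variation c = 0, 0.3 or 0.5. The robust variance is taken per participant. That is the natural reading of a count model with a person-time offset, and 7.3.7 describes the similar STI model woman by woman.

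**Closed form.** Relative to the squared mean, and treating follow-up as equal, the variance of a participant's count is:

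- without site: 1/m + k + c² + kc²
- within site: 1/m + k + kc²

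The ratio of reported standard errors, without site to with site, is the square root of the first over the second:

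- c = 0.3: √[(0.333 + 0.7 + 0.09 + 0.063)/(0.333 + 0.7 + 0.063)] = √(1.186/1.096) = 1.040
- c = 0.5: √[(0.333 + 0.7 + 0.25 + 0.175)/(0.333 + 0.7 + 0.175)] = √(1.458/1.208) = 1.099

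**Simulation.** 10,000 runs per setting, unequal site sizes, lognormal site rates, gamma-Poisson counts, log(person-time) offset:

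| | CV 0 | CV 0.3 | CV 0.5 |
|---|---|---|---|
| Mean reported SE of log rate ratio, without site | .0357 | .0381 | .0418 |
| Empirical SD, without site | .0359 | .0368 | .0384 |
| Mean reported SE, with site | .0356 | .0366 | .0382 |
| Empirical SD, with site | .0359 | .0367 | .0383 |
| Extra CI width without site | 0.3% | 4% | 9% |
| Actual alpha, without site | 0.052 | 0.044 | 0.035 |
| Actual alpha, with site | 0.052 | 0.051 | 0.050 |
| Power at rate ratio 1.12, without site | 89% | 86% | 80% |
| Power at rate ratio 1.12, with site | 89% | 87% | 85% |

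The Monte Carlo error for alpha is about 0.2 percentage points. The two estimators have practically the same empirical SD, so omitting site does not make the estimate less precise; it misreports the precision. Bias of the log rate ratio is at most .002 in every setting. At a rate ratio of 1.20, power is at least 99.5% either way.

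**Sensitivity.** Varying one input at a time (10 or 30 sites, overdispersion 0.3 or 1.5, mean 1 or 6), the interval is 2–7% wider at CV 0.3 and 5–15% wider at CV 0.5. For infrequent events the effect fades. At mean 0.2 per woman (0.2 × 3,350 = 670 events) it is 1% at CV 0.3 and 2% at CV 0.5. At mean 0.05 (about 167 events) it is under 1%.

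**Second simulation with different inputs.** 3,200 women, 20 sites, blocks of 8, participant variance 0.5, 1 event per person-year, 3,000 runs. At a site SD of 0, 0.3, 0.5 and 0.8 on the log scale, reported SE over true SD is 0.98, 1.06, 1.13 and 1.23, and actual alpha is 0.054, 0.038, 0.027 and 0.017. With site in the model, alpha is 0.046–0.055 throughout. With unstratified randomization instead, at site SD 0.5 and 0.8, the ratio without site is 1.00–1.01 and alpha 0.047–0.050. The shortfall therefore comes from stratifying by site and then omitting it.

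**The case against.** The strongest reply is that nothing in 7.3.2 is wrong. A treatment-only rate model with robust variance is a coherent marginal analysis, its estimate is unbiased, and it does not inflate type I error. The SAP's log-linear rate models all omit site, so this may be a convention rather than a lapse. The laboratory models offered as contrast are not reported in the CSR, and the acceptability models in 7.3.6 adjust for country rather than site. Little turns on this p-value: 7.3.2 relies on clinical judgment for individual event types, 7.2.4 sets no safety stopping rule, and 9.2 pools sites and describes safety reporting as descriptive. The size of the effect rests on assumed inputs, and nothing in the SAP shows that AE rates differ between sites.

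Most of this stands as a limit on importance. Two further limits also stand:

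- **Direction depends on the clustering unit.** Section 7.3.2 does not name it. Clustering on site would give an actual alpha of 0.065–0.10 with 10–20 sites, the opposite of conservative.
- **Step 1 gains almost nothing.** Five weeks at 3 events per 2.6 years is 3/2.6 × 5/52 = 0.11 events per woman. The closed form then gives ratios of only about 1.005 (CV 0.3) and 1.013 (CV 0.5).

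None of this removes the point. The SAP sets a formal alpha for this one comparison, and the test does not have that alpha when site rates differ.

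**Conclusion.** The point holds as a conditional one. If AE rates differ between sites and the robust variance is per participant, the comparison in 7.3.2 reports too large a standard error and is conservative. Under the base assumptions the interval is about 4% too wide at a between-site CV of 0.3 and 9% at 0.5. The power loss at a rate ratio of 1.12 is 1 and 5 percentage points, and there is almost none for a larger difference. These are illustrations, not estimates for this trial, because the between-site spread, overdispersion, event rate and number of sites are assumed. This is a nearly free improvement to the primary safety comparison, not a validity problem, and it should be made.

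**What to change.** Replace the duplicated comparison sentence in 7.3.2 with one along these lines: *The arms will be compared by a rate ratio with 95% CI and a test at alpha 0.05, from the log-linear model above with study site added as a categorical covariate; the robust variance is computed per participant.* Naming the participant only makes the natural reading explicit.

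Keep the treatment-only model for the descriptive arm-specific rates and their intervals, and keep the exact Poisson test for very rare events. Sections 7.3.3 and 7.3.4 inherit the change through their references back.

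The cost is one sentence and a table footnote saying that the ratio is site-adjusted. Site is already in the data. The adjusted ratio will not exactly equal the quotient of the two tabulated rates; in the simulation the difference was under 0.5% (CV 0.3) or 0.8% (CV 0.5) in 95% of runs. Sites without events need no pooling, because they contribute nothing to the rate ratio. In a check with 161 events and two of 20 sites with none, the log rate ratio was -0.0509 and its SE 0.1593 whether those sites were kept or dropped.
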